1.3. Evaluation of Secondary Endpoints (with and without hypotheses)

1.3.1. Control of Study-wise Type I Error

The Secondary Endpoints will be evaluated and tested only if the Primary Safety and Effectiveness hypotheses pass (i.e., both Primary non-inferiority tests reject the null hypothesis). Two of the 4 secondary endpoints will include a hypothesis test. They will be tested along with the inequality test of the Primary Efficacy Objective. The method of adjusting the α -level of the tests described below will be used to ensure that the study-wide error rate does not exceed 0.05.

The Hochberg method for controlling multiple comparison will be used. Two p-values will be obtained for the two Secondary Endpoints with hypothesis tests. If the larger p-value is less than 0.05, then both endpoints are considered statistical significant; otherwise, if the larger p-value is greater than 0.05, the smaller p-value need to be less than 0.025 to claim statistical significance for that endpoint with smaller p-value.

1.3.2. Analysis of the VCSS Pain Assessment

The first Secondary Objective is to evaluate whether the *VCSS Pain Assessment* of the BVS improves between the baseline classification and the follow-up classifications at 6, 12, 24, and 36 months. The

emphasis will be on the change between baseline and 12 months, since that is the time of the endpoint for the Primary Efficacy Objective. The four classes of VCSS for pain have been discussed previously in this Investigational Plan. (The VCSS includes clinical signs and symptoms other than pain, but this objective focuses only on pain.)

The objective is to demonstrate that the distribution of classifications improves from baseline to each follow-up time, especially at 12 months. This requires testing the null hypothesis (H_0) that the distribution at the 12-month follow-up ($D_{BVS@12M}$) remains unchanged compared to baseline ($D_{BVS@BL}$) against the alternative hypothesis (H_a) that the distribution shifts toward lower (less pain) classes:

$$H_0: D_{BVS@12M} \geq D_{BVS@BL} \quad \text{vs} \quad H_a: D_{BVS@12M} < D_{BVS@BL}$$

The endpoint for each study subject is the VCSS pain class at baseline and at each follow-up time (6, 12, 24, and 36 months).

Paired mean difference of the 12-month follow-up and baseline pain score and 95% CI will be presented. If the mean difference < 0 and the two-sided p-value from the paired t-test is deemed significant based on the appropriate α -level as described above, this will indicate success for this endpoint.

In addition, the VCSS pain class at each time point will be summarized descriptively..

1.3.3. Analysis of the Quality of Life (CIVIQ-20 Assessment)

The second Secondary Objective is to evaluate whether the *QoL Assessment* of the BVS improves between the baseline classification and the follow-up classifications at 6, 12, 24, and 36 months. The emphasis will be on the change between baseline and 12 months, since that is the time of the endpoint for the Primary Efficacy Objective. The QoL instrument will be the CIVIQ-20 and its use in the trial has been discussed previously in this Investigational Plan.

The objective is to demonstrate that the mean improves from baseline to each follow-up time, especially at 12 months. This requires testing the null hypothesis (H_0) that the mean score at the 12-month follow-up ($QoL_{BVS@12M}$) remains unchanged compared to baseline ($QoL_{BVS@BL}$) against the alternative hypothesis (H_a) that the mean is lower (better):

$$H_0: QoL_{BVS@12M} \geq QoL_{BVS@BL} \quad \text{vs} \quad H_a: QoL_{BVS@12M} < QoL_{BVS@BL}$$

The endpoint for each study subject is the CIVIQ-20 score at baseline and at each follow-up time (6, 12, 24, and 36 months).

The QoL hypothesis test:

$$H_0: QoL_{BVS@12M} \geq D_{BVS@BL} \quad \text{vs} \quad H_a: QoL_{BVS@12M} < D_{BVS@BL}$$

will be tested using a paired t-test with the appropriate α -level as described above.

In addition, descriptive statistics of total CIVIQ-20 score as well as score of each dimension at each time point will be presented by visit.

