
Primary Endpoint:
	
Safety: Freedom from Major Adverse Events (MAEs) through 30 days Defined as the following:
 
 • Device and/or procedure related death • Major amputation of target limb • Pulmonary Embolism which is clinically important (symptomatic with chest pain, hemoptysis, dyspnea, hypoxia, etc.) • Target Vessel Revascularization (TVR) • Vascular injury requiring surgical/endovascular intervention • Embolization/migration of stent • Device or procedure related acute DVT involving the treated limb 
Efficacy: Primary Patency rate at 12 months defined as Freedom from TVR; freedom from thrombus occlusion and stenosis $> 50\%$ as measured by DUS. Note: Venography will be used only if investigator cannot successfully measure endpoint by DUS or if the investigator deems there is clinical need to perform invasive venography.

Secondary Endpoints:
	
 - Evaluation of VCSS Scores at 30 days, 6, 12, 24, and 36 months - Quality of Life Questionnaire (QOL) at 30 days, 6, 12, 24, and 36 months - Evaluation of CEAP Scores at 30 days, 6, 12, 24, and 36 months - Acute Procedure Success - Lesion Success - Acute Technical Success - Freedom From Target Lesion Revascularization (TLR) at 30 days, 6, 24, 36 months - Freedom From Target Vessel Revascularization (TVR) at 30 days, 6, 24, 36 months - Primary Patency at 24, 36 months - X-ray analysis for stent fracture at 12, 24, and 36 months

Lead Principal Investigator:
	
[name] Thelma and Henry Doelger Professor (III) Department of Cardiothoracic Surgery Stanford University School of Medicine Falk Cardiovascular Research Center [name] [contact] [contact] Email: [contact]

European Co-Principal Investigator
	
[name] University Hospital Galway [name] [contact] Email: [contact]

Venographic Core Lab:
	
[name] Yale Cardiovascular Research Group [name] [contact]

Duplex Ultrasound Core Lab:
	
[name], MSc, MHA,FSVM, RPVI Vascular Ultrasound Core Lab Massachusetts General Hospital [name] [contact]

Please refer to Site Contacts List for all Sponsor, Investigator, and Vendor contact information.

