1 STATISTICAL ANALYSIS PLAN

1.1. Analysis Populations

Several populations of patients enrolled into the trial need to be defined.

The intent-to-treat (ITT) population consists of those subjects who have signed the Informed Consent Form and had the VENOVO™ Venous Stent catheter introduced (i.e., delivery system enters the subject's body).

Subjects who do not receive the study implant (section 5.2.2), but in whom the VENOVO™ Venous Stent catheter was introduced will be included in the ITT population. Subjects who need more than two (2) VENOVO™ Venous Stents (section 5.2.3) or undergo other treatment modalities (section 5.2.4) will be included in the ITT population.

A per-protocol (PP) population may be created if there are subjects who have any major protocol deviations. Major Protocol Deviations are defined as those that occur to protect the life or physical well-being of a subject in an emergency, or those that may affect the scientific soundness of the study, or the rights, safety or welfare of human subjects. The PP population will consist of any subjects in the ITT population who receive at least one stent and do not have any major protocol deviations, including deviations of study eligibility criteria. Subjects who need more than two (2) VENOVO™ Venous Stents, require placement of a commercially-available stent (section 5.2.3), or undergo other treatment modalities (section 5.2.4) will be excluded from the PP population.

All effectiveness and safety analyses including the primary analysis will be primarily based on the ITT population. A PP analysis may also be performed for the primary endpoint. It will only serve as a sensitivity analysis for the primary analysis which is based on the ITT population.

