1.4. Sample Size Consideration

Primary Efficacy Endpoints:

Table 6.3-1 shows the possible combinations of proportions of patients that could be enrolled in the study along with the weighted mean primary patency (PP) and the sample size required for 85% power against the PG (PP_{PG}).

Bard has chosen the sample size for the trial required for 85% power when the proportion of NIVL patients with endpoints is 20% and the proportion of PTS patients is 80%. This is the company's best guess for the actual enrollment. The estimate from the literature of the PP is 80% (used as the alternative proportion in the sample size estimate) and the PP_{PG} is 70% (used as the null proportion). The sample size is 138 patients. (This row is highlighted in yellow in Table 1.3-1.). With 45:55 split of the sample size, the PP_{PG} becomes 74%. As indicated in Table 6.3-1, the sample size required for 85% power will be between 121 and 125, which is less than planned sample size 138. In other words, with the same sample size as planned, >85% power can be achieved.

All sample size estimates in Table 1.3-1 were made with PASS 12 (Hintze, J. (2013). PASS 12. NCSS, LLC. Kaysville, Utah, USA. www.ncss.com) using the Fisher's Exact Binomial test for one proportion.

Note that the sample size of 138 patients is the number of evaluable patients. Up to 170 patients may be enrolled, depending on the losses-to-follow-up, deaths, and study withdrawals. Bard further estimates that approximately 50% of consented subjects will not meet the eligibility criteria (i.e., will

be Screen Failures), and therefore will not be enrolled in the study. The estimated consented population will therefore be 340 ($170/.5 = 340$).

Table 1.3 -1. Estimates of the Sample Size Based on the Proportions of NIVL and PTS Subjects in the Clinical Trial

NIVL %	PTS %	Weighted Mean PP	α	Performance Goal (PP _{PG})	Sample Size of BVS for 85% Power
5%	95%	77.9%	5%	68%	146
10%	90%	78.7%	5%	69%	140
20%	80%	80.4%	5%	70%	138
30%	70%	82.0%	5%	72%	132
40%	60%	83.6%	5%	74%	125
50%	50%	85.2%	5%	75%	121
60%	40%	86.9%	5%	77%	112

Primary Safety Endpoint:

The freedom-from-MAE rate estimated from the literature was 99%, which was used as the alternative proportion. The null proportion was the M_{PG} of 89%. With 42 BVS subjects, the study will have 85% power to detect a difference, and with 138 BVS subjects, the study power will be over 99%.

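### The 12-month VCSS-pain and CIVIQ-20 tests use only subjects scored at 12 months and ignore the 30-day and 6-month scores, so the mean improvement is biased if leaving is related to earlier response

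*Combined protocol and SAP*

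**What the plan says.** - **Tests.** For VCSS pain, SAP 1.3.2 states: "Paired mean difference of the 12-month follow-up and baseline pain score and 95% CI will be presented". Success is declared on this condition: "If the mean difference < 0 and the two-sided p-value from the paired t-test is deemed significant". For CIVIQ-20, SAP 1.3.3 says the 12-month hypothesis "will be tested using a paired t-test with the appropriate" α-level. Neither section names a method for missing scores.
- **Multiplicity.** SAP 1.3.1 applies Hochberg to the two tests, and only after both co-primary endpoints succeed: "If the larger p-value is less than 0.05, then both endpoints are considered statistical significant".
- **Scores collected.** The protocol summary lists "Evaluation of VCSS Scores at 30 days, 6, 12, 24, and 36 months" and "Quality of Life Questionnaire (QOL) at 30 days, 6, 12, 24, and 36 months". Sections 1.3.2 and 1.3.3 start the follow-up series at 6 months and omit 30 days. Scores at visits other than baseline and 12 months are only summarised.
- **Population.** SAP 1.1: "All effectiveness and safety analyses including the primary analysis will be primarily based on the ITT population".
- **Missing data.** The only text is SAP 1.2.3, placed under the primary endpoints. It takes analysis of the subjects who contribute endpoints as the standard and calls this unbiased for event rates when missingness is unrelated to the intervention and to the data. It allows a worst-case analysis that assumes failure at censoring, requires a tipping-point analysis in every case, and says multiple imputation will be explored.
- **Planned loss.** SAP 1.4: "Note that the sample size of 138 patients is the number of evaluable patients". Up to 170 may be enrolled to allow for losses, deaths and withdrawals.

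**The concern.** A paired t-test needs both scores. A subject seen at 30 days and 6 months but not at 12 months is therefore deleted, together with the information on how that subject was doing. The completer mean estimates the ITT mean only if leaving is unrelated to response. There is no control arm in which such a bias could partly cancel.

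At stake are the only two secondary results that carry a hypothesis test, and the size of benefit reported from them. Scores already scheduled could remove the part of the bias that they explain.

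**Working it through.** **1. The plan's own figure.** The 138 in SAP 1.4 is for 12-month patency: exact one-sample binomial, 70% against 80%, one-sided 0.05, 85% power. It reproduces: success at 106 or more of 138 has alpha 0.0466 and power 0.851. No sample size, power, SD or expected change is given for either score test.

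**2. Ceiling on loss.** 170 − 138 = 32, and 32/170 = 18.8%. This is the most that the plan allows for patency, not a forecast for the scores, so 10% is shown as well.

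**3. General formula.** Completer bias = share missing × (mean change in leavers − mean change in completers). At 18.8%, gaps of 0.25, 0.5 and 1.0 SD give 0.188 × gap = 0.05, 0.09 and 0.19 SD. If leavers had no change at all, the completer mean would exceed the all-subject mean by 170/138 − 1 = 23%.

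**4. Dropout driven by the 6-month change.** Assumptions, none from the documents: the 6- and 12-month changes are normal with SD 1 and correlation r; leaving follows a logistic model in z, the standardised 6-month change (higher = worse), with the odds ratio (OR) shown per SD. Then completer bias = r × mean of z among those who stay. Integrating over the normal distribution, with the intercept set to give the stated loss:

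| Loss | OR per SD | Mean z in stayers | Bias, r = 0.5 | Bias, r = 0.7 |
|---|---|---|---|---|
| 18.8% | 1.6 | −0.086 | −0.04 | −0.06 |
| 18.8% | 2.3 | −0.142 | −0.07 | −0.10 |
| 18.8% | 3.3 | −0.186 | −0.09 | −0.13 |
| 10% | 1.6 | −0.046 | −0.02 | −0.03 |
| 10% | 2.3 | −0.078 | −0.04 | −0.05 |
| 10% | 3.3 | −0.104 | −0.05 | −0.07 |

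Negative means too favourable. If CIVIQ-20 change had an SD of 20 points (assumed), the 18.8% range would be 0.043 × 20 = 0.9 to 0.130 × 20 = 2.6 points. If better responders leave, the signs reverse; if leaving is unrelated to response, the bias is zero.

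**5. What the earlier scores recover.** In 1,000 simulated trials per scenario (N = 170, 18.8% missing, correlation 0.5 from baseline to follow-up and 0.7 among follow-ups), the completer mean was compared with a likelihood estimate that uses the baseline, 30-day and 6-month scores. The log-odds slopes per SD were 0.5, 1 and 2; the last is stronger than anything in the table.

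| Leaving depends on | Completer bias (SD) | Bias using earlier scores (SD) |
|---|---|---|
| Observed 6-month change | 0.06, 0.11, 0.17 | within about 0.005 |
| Unseen 12-month change | 0.09, 0.16, 0.25 | 0.04, 0.07, 0.12 |

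The near-zero result in the first row is built in, because leaving was generated from a score that the estimate conditions on. The second row is the fairer warning: roughly half the bias remains.

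**6. Effect on the claim.** With no true change, the chance of a false claim of improvement (nominally 2.5% in that direction) rose to about 11% and 26% at slopes 0.5 and 1 on the 6-month change. With a true improvement of 0.8 SD, the test was significant in every scenario; only the reported size moved.

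**The case against.** The strongest reply is that SAP 1.2.3 already deals with missing data. It opens by speaking of study endpoints in general, requires reasons for missingness to be reported, and makes a tipping-point analysis mandatory. That analysis can address dropout that depends on unseen scores, which a mixed model cannot. A reader might infer from 1.3.2 and 1.3.3 alone that the plan has no safeguard, and the documents do not support that. But the scope of 1.2.3 over these scores is unclear, and a failure assumed at censoring has no meaning for a change in pain class or CIVIQ-20. Even on the generous reading, it adds a sensitivity analysis and leaves the deciding tests on completers.

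A reader might also infer that 19% of the scores will be missing. The documents do not say so: 138 is an evaluable count for patency, 170 is a ceiling, and a subject without a usable scan may still have both scores.

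Other points stand and limit the weight. The direction of bias is assumed. A paired t-test on change is conventional. These are secondary tests, reached only after both primaries succeed. A mixed model implicitly assigns 12-month scores to subjects who have died, so it needs a stated rule for deaths. VCSS pain has four ordered classes, but the paired t-test already treats it as numeric.

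**Conclusion.** The point holds as a conditional one. The two tests use completers only and set aside scheduled 30-day and 6-month scores, so the mean improvement is biased whenever leaving is related to earlier response. Under the stated assumptions the completer mean is too favourable by about 0.04 to 0.13 SD at the maximum planned loss of 18.8%, and by about 0.02 to 0.07 SD at 10% loss. The odds ratios, correlations, direction and SD are all assumptions.

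Two stronger readings should be resisted. One is that the significance claims are unsafe: that applies only if the true change is near zero, and with a large improvement the harm is to the reported size of benefit. The other is that a repeated-measures model removes the bias: it does so only when leaving depends on scores that were seen. The primary safety and patency conclusions are unaffected. The change is worth making because it is cheap and rests on a weaker assumption than the present test.

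**What to change.** 1. In 1.3.2 and 1.3.3, test the 12-month minus baseline contrast from a mixed model for repeated measures: scores at baseline, 30 days, 6 and 12 months as responses, visit as a factor, unstructured covariance, all ITT subjects with a baseline score. Test two-sided at the same Hochberg levels.
2. Keep the paired t-test as a supportive analysis.
3. Add the 30-day score to the follow-up times in both sections, to match the protocol summary.
4. State that the 1.2.3 tipping-point analysis applies to these two scores, defined as a shift added to the missing 12-month scores and increased until the conclusion changes.
5. State how deaths before 12 months are handled.

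Cost: SAP wording and standard programming, with no new data or visits. The downside is reliance on missing-at-random. This is weaker than what the t-test needs, but it corrects only part of the bias when leaving depends on the unseen 12-month score, which is why item 4 belongs with item 1.

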1.3.4. Analysis of the CEAP Scores

The third Secondary Objective is to assess the CEAP scores at baseline, 6, 12, 24, and 36 months. Each classification factors at each time points will be summarized descriptively. No hypotheses will be tested.

1.3.5. Analysis of other Secondary Objective

The following secondary endpoints are intended to be reported in the device's labeling and will be summarized using descriptive statistics (sample size of reported values, means or proportions, standard deviations, and 95% confidence intervals). The details of the definition of the secondary endpoints are described in Section 3.2.

- Acute Procedure Success
- Lesion Success
- Acute Technical Success
- Target Lesion Revascularization (TLR)
- Target Vessel Revascularization (TVR)
- Patency at 24 and 36 months
- X-ray analysis for fracture at 12, 24, and 36 months

1.4. Sample Size Consideration

Primary Efficacy Endpoints:

Table 6.3-1 shows the possible combinations of proportions of patients that could be enrolled in the study along with the weighted mean primary patency (PP) and the sample size required for 85% power against the PG (PP_{PG}).

Bard has chosen the sample size for the trial required for 85% power when the proportion of NIVL patients with endpoints is 20% and the proportion of PTS patients is 80%. This is the company's best guess for the actual enrollment. The estimate from the literature of the PP is 80% (used as the alternative proportion in the sample size estimate) and the PP_{PG} is 70% (used as the null proportion). The sample size is 138 patients. (This row is highlighted in yellow in Table 1.3-1.). With 45:55 split of the sample size, the PP_{PG} becomes 74%. As indicated in Table 6.3-1, the sample size required for 85% power will be between 121 and 125, which is less than planned sample size 138. In other words, with the same sample size as planned, >85% power can be achieved.

All sample size estimates in Table 1.3-1 were made with PASS 12 (Hintze, J. (2013). PASS 12. NCSS, LLC. Kaysville, Utah, USA. www.ncss.com) using the Fisher's Exact Binomial test for one proportion.

Note that the sample size of 138 patients is the number of evaluable patients. Up to 170 patients may be enrolled, depending on the losses-to-follow-up, deaths, and study withdrawals. Bard further estimates that approximately 50% of consented subjects will not meet the eligibility criteria (i.e., will

be Screen Failures), and therefore will not be enrolled in the study. The estimated consented population will therefore be 340 ($170/.5 = 340$).

Table 1.3 -1. Estimates of the Sample Size Based on the Proportions of NIVL and PTS Subjects in the Clinical Trial

NIVL %	PTS %	Weighted Mean PP	α	Performance Goal (PP _{PG})	Sample Size of BVS for 85% Power
5%	95%	77.9%	5%	68%	146
10%	90%	78.7%	5%	69%	140
20%	80%	80.4%	5%	70%	138
30%	70%	82.0%	5%	72%	132
40%	60%	83.6%	5%	74%	125
50%	50%	85.2%	5%	75%	121
60%	40%	86.9%	5%	77%	112

Primary Safety Endpoint:

The freedom-from-MAE rate estimated from the literature was 99%, which was used as the alternative proportion. The null proportion was the M_{PG} of 89%. With 42 BVS subjects, the study will have 85% power to detect a difference, and with 138 BVS subjects, the study power will be over 99%.

Overall study power: with taking into consideration of both co-primary efficacy and safety endpoints, with 138 BVS subjects, the overall study power is at least $85\% * 99\% = 84\%$.
